Appendix 2 Schedule of Assessments (cont.)

- ⁱ Laboratory data (performed locally) includes complete blood count with differential and serum chemistries (i.e., sodium, potassium, chloride, glucose, blood urea nitrogen, creatinine, calcium, phosphorus, magnesium, creatine phosphokinase, total protein, albumin, creatinine, total and direct bilirubin, alkaline phosphatase, ALT, and AST). Female patients of childbearing potential will be required to have a negative serum pregnancy test result at screening and urine pregnancy tests performed at Weeks 13, 25, 37, and 49; every 12 weeks starting from Week 57; and study completion/early termination.
- ^j When blood is drawn via catheter or CVAD, a discard tube must be used prior to collection of samples for any laboratory assessment, due to the possibility of contamination by saline or anticoagulants used to flush the device. Please consult the study Laboratory Manual for details on sample collection and processing.
- ^k Anti-FVIII antibodies will be measured at a central laboratory using citrate plasma. Anti-FVIII antibodies is the only biomarker sample taken at screening. In case a patient screen fails or does not enroll in the study for any reason, the sample should be destroyed and not sent to the central laboratory. Throughout the study, additional blood samples may also be drawn on an unscheduled basis (at the clinical judgment of the investigator) for analysis at a central laboratory.
- ^l Samples to detect anti-emicizumab antibodies will be collected prior to emicizumab injection at Weeks 1, 5, 17, 33, 49, every 12 weeks starting from week 57, study completion/early termination and at the 24-week safety follow-up visit. If patients continue on emicizumab past 52 weeks of treatment, anti-emicizumab antibodies will be collected every 12 weeks. If any of these samples are positive and/or if there is suboptimal clinical response or low pharmacokinetic exposure, additional samples may be collected and analyzed for anti-emicizumab antibodies. Anti-emicizumab antibodies should also be drawn at the time of systemic hypersensitivity events. For each additional anti-emicizumab sample, a PK sample should be concomitantly drawn.
- ^m At the Week 1 visit, caregivers will be trained on how to use their handheld device to record the bleeds and the hemophilia medication use. The bleeding/medication questionnaire will be completed by the caregiver and includes start date and time, reason, type, location of each bleed, as well as start date and time, reason, type, and dose of each injection.
- ⁿ Caregivers will be instructed to complete on weekly basis to complete the bleed/medication questionnaire when the patient has a bleed or hemophilia medication use.
- ^o At subsequent visits as marked, investigator review of patient-reported bleed/medication questionnaire information will be conducted for completeness and accuracy.
- ^p Following bypassing agent treatment, patients should provide a sample for local laboratory monitoring of thromboembolic events and thrombotic microangiopathy for platelet count, serum creatinine, LDH, and schistocytes within 24–48 hours of initial bypassing agent use. A plasma sample should also be provided for local (one aliquot) and central (a second aliquot) laboratory monitoring of fibrinogen, prothrombin fragment 1+2, and D-dimer. If prothrombin fragment 1+2 test cannot be done at the site, the sample should be send to the local reference laboratory, if available, and if the results from the local reference laboratory can be obtained within a reasonable timeframe to allow for decision making. For patients who require multiple doses of bypassing agents, laboratory monitoring should be performed every 24–48 hours thereafter until 24–48 hours following the last dose of bypassing agents administered to treat a given bleed. If applicable, laboratory results should be recorded in the eCRF page titled “Local Lab Following Treatment with Bypassing Agents.”

Appendix 2 Schedule of Assessments (cont.)

- ^q Patients are advised to inform the investigator about adverse events at every visit. Adverse events will be reported on the eCRF by the investigator. Injection-site reaction adverse events will be collected on a separate form from the adverse event form. If there is unexpected worsening of the patient's hemophilia in terms of severity (e.g., increased number of doses of bypassing agents to stop bleeds compared with before study entry), frequency of bleeds, or nature at any time during the study, this should be documented as an adverse event on the Adverse Event eCRF, conveying that the underlying condition has changed by including applicable descriptors (e.g., "increased clinical severity of hemophilia").
- ^r Drug accountability will not be performed at the first visit of emicizumab receipt. Drug dispensation will not occur at the study completion/early termination visit. *Note: for Cohort C, there are visits where emicizumab is not administered per schedule.*
- ^s Haemo-QoL-Short Form (children 8 years of age and older) assessed on an electronic, handheld device by patients during patient's visit in clinic prior to emicizumab injection at Weeks 1, 13, 25, 37, 49, every 24 weeks from Week 57, and study completion/early termination.
- ^t Proxy assessment of HRQoL and aspects of caregiver burden using the Adapted InhibQoL Including Aspects of Caregiver Burden questionnaire for all children assessed on electronic, handheld device by caregivers during patient's visit in clinic prior to emicizumab injection at Weeks 1, 13, 25, 37, 49, every 24 weeks from Week 57 and study completion/early termination.
- ^u Emicizumab concentration. Plasma samples for this assessment should be taken prior to emicizumab injection.
- ^v PD biomarkers will be measured at a central laboratory. See [Appendix 3](#), for detailed explanation of PD biomarker assessments. Blood samples may also be drawn to conduct biomarker assays at the central laboratory on an unscheduled basis (at the clinical judgment of the investigator) at any time.

Appendix 3 Schedule of PD Assessments

Sample	Visit ^a	Biomarker assays ^b
PD Set 1	Weeks 1, 3, 5, 9, 13, 17, 21, 25, 29, 33, 37, every 8 weeks from Week 41, every 12 weeks from Week 57 Study Completion/Early Termination Safety Follow-up Visit Unscheduled visit (at the discretion of the investigator) while on emicizumab ^c	PT/INR D-dimer aPTT
PD Set 2 ^d	Weeks 1, 3, 5, 9, 13, 17, 21, 25, 29, 33, 37, every 8 weeks from Week 41, every 12 weeks from Week 57 Study Completion/Early Termination Safety Follow-up Visit Unscheduled visit (at the discretion of the investigator) while on emicizumab ^c	FVIII activity FIX antigen FX antigen

FIX=factor IX; FVIII=factor VIII; FX=factor X; PD=pharmacodynamic.

^a All samples are to be collected on Day 1 of the indicated week, prior to emicizumab injection (if applicable). All PD samples will be citrate plasma.

^b Biomarker assays will include but are not limited to those listed. Where blood volumes allow, additional plasma may be frozen and banked for future exploratory research related to emicizumab. Blood volumes and processing procedures will be specified in the Laboratory Manual.

^c Reasons for unscheduled visits may include evaluation or treatment for bleeds or hypersensitivity reactions.

^d These plasma samples will only be collected if the permitted blood volumes allow (based on patient body weight as described in Protocol Section 3.3.5). Please refer to the Laboratory Manual for details.

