3.3.5 Rationale for Biomarker Assessments

Some biomarkers to measure the PD effect of emicizumab on hemostasis have not been fully validated to date and require further testing to determine which assays and technical conditions are most suitable for use with emicizumab treatment. Refer to Section 5.1.3 for more information about effects of emicizumab on existing laboratory assays. Plasma samples will be collected for central PD biomarker assessment in parallel with PK samples to demonstrate evidence of biologic activity of emicizumab in patients and to monitor the patients' coagulation status. These biomarkers include but are not limited to coagulation-related assays such as aPTT, PT/INR, D-dimer, and FVIII activity assays. The aPTT and thrombin generation assays were previously shown in the Phase I/II study to exhibit a dose-response relationship to emicizumab concentration (for more information, see the Emicizumab Investigator's Brochure). The central aPTT assay will be run both in standard form and with a modification to ensure that the assay range covers all levels of emicizumab exposure.

Exploratory plasma biomarkers will include factor IX antigen (FIX:Ag) and factor X antigen (FX:Ag) to assess whether drug treatment causes a change in the circulating levels of these coagulation factors, which are the binding targets of emicizumab, and may include measurement of other coagulation or hemophilia-related factors or assays. Finally, residual blood from collected samples may be used for additional emicizumab-related research. These banked plasma samples will not be used for general, disease-related research purposes but instead for research directly related to emicizumab.

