Assessments that require blood draws should be monitored closely to ensure that institutional mandates regarding total sample blood volumes are followed. In situations where no institutional guidance is available, the following limits should be utilized and have been included in the design of the sampling program: no more than 1% of the total blood volume should be taken at one time and no more than 3% of the total blood volume should be taken over a 30 day period. (Total blood volume is defined as 80–90 mL/kg [European Union 2008]). Thus, blood sampling timepoints and volumes follow the EC Guideline on Ethical considerations for clinical studies on medicinal products conducted with the pediatric population. In situations where the total volume of blood drawn might exceed the limits stated above, clinical (safety) laboratory assessments should be prioritized. Any remaining permitted blood volume should be collected for PK and immunogenicity samples, followed by biomarker and PD samples. Refer to the laboratory manual for detailed weight-based blood sampling guidelines.

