4.7 BIOMARKER ANALYSIS

Pharmacodynamic (PD) parameters (e.g., aPTT, FVIII activity) and other exploratory markers (FIX and FX antigens, PT/INR, D dimer) will be presented using summary statistics, including means, median, range, standard deviations, and coefficients of variation. In addition, individual patient plots will be provided. At the time of the interim analysis, only listings and patient plots will be performed.

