Appendix 1 Protocol Synopsis (Cont)

Pharmacokinetic Analyses

For all patients, pre-dose (trough) plasma concentrations of emicizumab will be presented descriptively by dose groups (1.5 mg/kg QW, 3 mg/kg Q2W, 6 mg/kg Q4W, 3 mg/kg QW in case of up-titration), including arithmetic and geometric means, median, range, standard deviations, and coefficients of variation.

Nonlinear mixed effects modeling will be used to analyze the dose-concentration-time data of emicizumab following SC administration. Population PK parameters, such as clearance and volume of distribution, will be estimated, and the influence of various covariates, such as age, sex, and body weight, on these parameters will be investigated graphically. Secondary PK parameters, such as area under the curve, will be derived from individual post-hoc predictions. Data may be pooled with data from previous Phase I/II studies and Phase III Studies. These analyses will be reported in a dedicated report.

Patient-Reported Outcome Analyses

Scale scores for the Haemo-QoL-SF and the Adapted InhibQoL Including Aspects of Caregiver Burden will be calculated for each assessment, with change scores being examined for the assessments over the course of the study. These will be summarized descriptively by cohort. A descriptive summary of the number of daycare/school days missed and days hospitalized will also be presented by cohort.

Pharmacodynamic Biomarker Analyses

PD parameters (e.g., aPTT, FVIII activity) will be presented using summary statistics by dose groups, including arithmetic and geometric means, median, range, standard deviations, and coefficients of variation. These analyses will be presented by cohort.

Interim Data Review

In a first interim data review, the appropriateness of the initial dosing regimen will be evaluated (maintenance dose of 1.5 mg/kg/week). This dosing regimen may be adapted following analysis of all available data (e.g., safety, efficacy, pharmacokinetics) by the JMC (see protocol) if a majority of the first 3–5 patients (aged ≥ 2 to < 12 years of age) fail to achieve optimal control of bleeds after the first 12 weeks of treatment; or if their plasma emicizumab concentration trough level is lower than the one being targeted in adolescents and adults (i.e., 45 µg/mL). Should patients ≥ 12 years of age and < 40 kg be enrolled at the time of this first interim data review, available data from these patients will also be included.

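### The plan gives no numerical estimate of the FIX and FX antigen change that the protocol sets out to assess, and weight-dependent sampling makes differences in mean level an unsafe substitute

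*SAP*

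**What the plan says.** **Purpose.** Protocol 3.3.5 lists FIX and FX antigen as exploratory plasma markers, measured "to assess whether drug treatment causes a change in the circulating levels of these coagulation factors".

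**Analysis.** Under SAP 4.7 these antigens and the other PD markers "will be presented using summary statistics, including means, median, range, standard deviations, and coefficients of variation". Individual patient plots are added. The synopsis in SAP Appendix 1 is similar: "PD parameters (e.g., aPTT, FVIII activity) will be presented using summary statistics by dose groups". Protocol 6.8 adds geometric means and presentation by cohort. None of these sections mentions change from baseline, and SAP 4.7 names no timepoint, whereas SAP 4.5 does so for drug concentrations.

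**Collection.** PD Set 2 (FVIII activity, FIX antigen, FX antigen) is scheduled pre-dose at Weeks 1, 3, 5 and 9 and regularly thereafter. Footnote d in SAP Appendix 3, repeated in Protocol Appendix 2, makes it conditional: "These plasma samples will only be collected if the permitted blood volumes allow". Where no institutional guidance exists, Protocol 3.3.5 sets two limits. One governs each single draw: "no more than 1% of the total blood volume should be taken at one time". The other is cumulative across visits: "no more than 3% of the total blood volume should be taken over a 30 day period". Safety laboratory tests come first when the limit is reached, and then: "Any remaining permitted blood volume should be collected for PK and immunogenicity samples, followed by biomarker and PD samples".

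**The concern.** The question for FIX and FX antigen is whether a child's level moves after treatment starts. The planned tables describe levels. A reader who wants the change has to subtract one mean from another, or judge it by eye from individual plots.

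Subtracting means is safe only if the same kind of child contributes to both. Set 2 depends on body weight, is last in priority, and is collected in a study that admits children from just over 3 kg (Protocol 4.2). If the share of light children differs between two visits, and light children have different antigen levels, the means differ with no drug effect. A real change could also be masked.

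At stake is an exploratory question about the drug's binding targets. No efficacy, safety or dosing decision in the documents rests on it.

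**Working it through.** The plan gives no figure to reproduce here. The check has four steps.

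**1. Where the SAP plans change and where it does not.** Change from baseline is specified for vital signs (SAP 4.6.4), ECG (4.6.5) and quality-of-life scores (4.4.1.3), and as shift tables for laboratory data (4.6.3). It is absent from 4.7, although change is the stated purpose for FIX and FX antigen and a Week 1 pre-dose sample is already scheduled.

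**2. The blood limits per kilogram.** Input from Protocol 3.3.5: "Total blood volume is defined as 80–90 mL/kg".
- Single draw: 1% × 80–90 = 0.8–0.9 mL/kg.
- 30 days: 3% × 80–90 = 2.4–2.7 mL/kg.

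**3. Can the children sampled differ between visits?** Weeks 1 to 5 place five visits on Days 1, 8, 15, 22 and 29, inside one 30-day window. From Week 9 at most three visits fall in any 30 days, and 3 × 1% = 3%, so only the single-draw cap applies. Draw volumes are not in the documents. Assume an equal volume V at each visit. One draw needs a weight of at least V ÷ (0.8 to 0.9). All five early draws need at least 5V ÷ (2.4 to 2.7).

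| V (assumed) | One draw | All five early draws |
|---|---|---|
| 2 mL | 2.2–2.5 kg | 3.7–4.2 kg |
| 5 mL | 5.6–6.2 kg | 9.3–10.4 kg |
| 10 mL | 11.1–12.5 kg | 18.5–20.8 kg |

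A child between the two thresholds can give a full draw at a later visit but not at all five early ones. Something must then be left out, and Set 2 is last in line. The documents do not say at which visit. Equal volumes are a simplification, because Set 2 is due at only three of the five visits.

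**4. How far could means move with no drug effect?**

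Shift = (share of light children at the visit − share at Week 1) × (mean of light − mean of heavier children).

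Illustrative assumptions, none from the documents: 60 children, 18 of them light; all heavier children sampled; light children sampled at 30% at Week 1 and 90% later.
- Share at Week 1: 5.4 ÷ (42 + 5.4) = 0.114.
- Share later: 16.2 ÷ (42 + 16.2) = 0.278.
- Difference in share: 0.164.
- Shift if light children are 10 units lower: 0.164 × (−10) = −1.6.
- Shift if 20 units lower: 0.164 × (−20) = −3.3.

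A simulation of 4,000 repetitions (heavier-child mean 80, between-child SD 12, within-child SD 6, no drug effect) gave −1.63 and −3.34 for the difference of means. Mean within-child change was 0.04 and −0.01. With equal sampling at both visits, or with no light–heavy difference, both methods gave about zero. If light children were instead the better sampled at Week 1, the sign would reverse. A wider grid, with share differences up to 0.30 and level differences up to 20 units, runs from 0 to 0.30 × 20 = 6 units in size.

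**The case against.** The strongest reply is that nothing in the documents shows a problem of any size. Protocol 3.3.5 says the limits were built into the sampling design, the volumes are in a manual not available here, and the 1% and 3% limits apply only where an institution has no rule of its own. Children under 2 years, probably the lightest, are planned at about 5 (SAP 2.4) or 5–10 (Protocol 4.1) of roughly 80. SAP section 4 already promises the number of observations for every variable. All of this stands, and it is why the magnitude above is only an illustration.

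Four stronger readings are tempting and are not supported.
- *The plan cannot show any change in FIX or FX.* The individual plots show each child's course. What is missing is a numerical summary.
- *Visit means do come from different children.* They can; the documents do not show that they do, and visit means are themselves inferred, since SAP 4.7 names no timepoint.
- *The limits bind hardest at Week 1, so light children are missing from baseline.* Dividing 3% evenly over five visits gives 0.6% each (0.48–0.54 mL/kg), which suggests this, but no section prescribes an even split. If the screening draw respected the 1% cap, at least 3% − 1% = 2% remains at Week 1. The single-draw cap then applies, as it does later. Unless sites ration in advance, a shortage falls later in loading.
- *The argument covers all PD markers.* The change aim is stated for FIX and FX antigen only, not for FVIII activity. The aPTT, PT/INR and D-dimer samples are PD Set 1, to which footnote d does not apply.

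**Conclusion.** The point holds in limited form. For FIX and FX antigen the protocol asks about change, and the SAP provides level summaries and plots without a numerical estimate of that change. This follows from the text alone and needs no assumption.

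The second part is conditional. A difference in mean level misleads only if the mix of children shifts between visits and antigen level varies with weight. The first is possible under the stated limits. The second has only indirect support: Protocol 3.3.1 describes a functioning coagulation system, including FIX and FX, from 6 months of age, which suggests that younger infants may differ. The illustrated shift of 1.6 to 3.3 units, and the range of 0 to 6, rest wholly on assumed shares and level differences, and zero is a possible answer.

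Severity is low: an exploratory marker in a descriptive study, with a better summary available from samples already scheduled.

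**What to change.** In SAP 4.7, for FIX antigen and FX antigen, add a by-visit summary of within-child change from the Week 1 pre-dose sample, in children with a sample at both times. Beside it, give the number and body weight of the children included and of those not sampled at that visit or at Week 1. Keep the planned level summaries and individual plots.

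The cost is a few table columns. No extra blood, visit or data item is needed.

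There are two limitations to state with the table. Children without a Week 1 Set 2 sample do not contribute, so if light children are the ones missing, the estimate describes mainly the heavier ones; the body-weight figures make that visible. In the youngest infants, change from Week 1 may include normal maturation as well as any drug effect.
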